**Table 1: Schedule of Events (Laboratory and Clinical)**

Time - Months (+/- 14 Days)	9	12	15	18	21	24	30	36	42	48	54	60	YEARLY	6-15
Overall Survival (OS)		X				X		X		X		X		X
Disease-Free Survival (DFS)		X				X		X		X		X		X
Relapse-Free Survival (RFS)		X				X		X		X		X		X
Hematology; Chemistry	X	X	X	X	X	X								
Immune Reconstitution  :	X	X	X	X	X	X								
RCR 	X	X	X	X	X	X	X	X	X	X	X	X		X
Modified History & Physical	X	X	X	X	X	X	X	X	X	X	X	X		X
Neurological Exam 	X	X	X	X	X	X	X	X	X	X	X	X		X
Vital Signs 	X	X	X	X	X	X								
GVHD Assessment 	X	X	X	X	X	X								
Concomitant Medication 	X	X	X	X	X	X								
Adverse Event	X	X	X	X	X	X	X	X	X	X	X	X		X
Bellicum Research Samples	BPX-501 T cell Assessment Research samples for assessment of BPX-501 cells (CD3+CD19+) will be collected monthly ( $\pm$ 14 days) until 1-year post BPX-501 infusion, every 6 months ( $\pm$ 1 month) for 24-months post BPX-501 infusion.													
	Post-systemic corticosteroid administration: Research samples (peripheral blood and/or tissue) for assessment of BPX-501 cells (CD3+CD19+) will be collected and sent to the sponsor prior to administration of systemic corticosteroids doses (e.g. methylprednisolone), at 4-hours ( $\pm$ 30 minutes) and 24-hours ( $\pm$ 1 hour) post-systemic corticosteroid initiation, and at 7-days, 14-days, 21-days, and 28-days ( $\pm$ 24 hours) post-systemic corticosteroid initiation.													
Rimiducid Infusion 	BPX-501 Cellular Kinetics (post-rimiducid) Within 4 hours ( $\pm$ 30 minutes) prior to initiation of rimiducid infusion, 30 minutes ( $\pm$ 5 minutes), then at 2 hours, 4 hours, 6 hours, 8 hours, 12 hours, and 24 hours ( $\pm$ 30 minutes) after initiation of infusion (of each dose of rimiducid) samples will be collected (and will be split for separate processing). Subsequently at 48 hours ( $\pm$ 1 hour) and 7 days (after initiation of infusion of each dose of rimiducid), and then at 14 days, 21 days, and 28 days ( $\pm$ 24 hours) after the final dose of rimiducid (if more than one dose is administered) blood samples will be drawn and evaluated for T cell responses only.													
	Rimiducid Pharmacokinetics (PK): As achievable, blood samples will be drawn at the following time-points (in the same series as the split samples above): within 4 hours ( $\pm$ 30 minutes) prior to the initiation of rimiducid infusion; 30 mins ( $\pm$ 5 minutes) after initiation of the infusion; at 2 hours (< 5 min prior to end of the rimiducid infusion), 4 hours, 6 hours, 8 hours, 12 hours, and 24 hours ( $\pm$ 30 minutes) after the start of the infusion. (see Appendix F ).													

1 Peripheral blood (~12 mL, in green top tubes; as feasible for patient weight) shall be collected for Immune Reconstitution and clinical flow cytometry studies. The basic clinical flow panel includes CD3+ cells, (if achievable, alpha/beta CD3+ cells, gamma/delta CD3+ cells), CD4+ cells, CD8+ cells, Natural Killer cells, B cells, and CD3+/CD19+ cells, CD3+/CD19+/CD4+ cells and CD3+/CD19+/CD8+ cells. Additional flow panels may be included as deemed necessary by the treating physician. IgG, IgM and IgA levels shall be reported.

2 Vital signs include blood pressure, heart rate, respiratory rate and temperature.

3 Concomitant Medication: The protocol will be conducted during the routine clinical care of the patients. All treatments and critical medications, defined below shall be collected in the EDC database:

- Treatment for GVHD
- Prophylaxis and/or treatment for infectious complications
- Treatments in association with serious adverse events (SAE)s

Standard supportive care treatments, non-prescription medications/OTCs, NSAIDs, laxatives/stool softeners, vitamins, and herbal supplements will not be collected if they are not protocol-mandated.

4 Two purple top tubes (heparinized) of whole blood to be collected and frozen and then batch shipped to the Sponsor or designee per instructions in the laboratory manual for collection of the gene therapy monitoring.

5 For clinical assessment and management of neurotoxicity refer to [Appendix E](#).

6 GvHD assessments will be performed according to standard practice in the hospital. Refer to [Appendix A](#) and [Appendix B](#).

7 Research blood sample collection for rimiducid infusion to be sent as directed. Refer to [Appendix F](#) for collection and processing of samples for pPK testing.

### 3 LIST OF ABBREVIATIONS AND TERMS

AE	Adverse Event
aGVHD	Acute Graft Versus Host Disease
Allo-HSCT	Allogeneic hematopoietic stem cell transplantation
CFR	Code of Federeal Regulations
cGVHD	Chronic Graft Versus Host Disease
CNS	Central Nervous System
CRF	Case Report Form
CRO	Contract Research Organization
CTL	Cytotoxic T Lymphocytes
DFS	Disease Free Survival
eCRF	Electronic Case Report Form
DEHP	Bis(2-ethylhexyl) phthalate
EC	Ethics Committee
EDC	Electronic Data Capture
EMA	European Medicines Agency
FDA	Food and Drug Administration
FKBP	Human FK-506-binding protein
GCP	Good Clinical Practice
GI	Gastrointestinal
GVHD	Graft Versus Host Disease
HLA	Human Leukocyte Antigens
HSV	Herpes Simplex Virus
iCasp 9	Inducible Caspase 9
ICH	International Conference on Harmonization
IMP	Investigational Medicinal Product
IRB	Institutional Review Board
IV	Intravenous
LTFU	Long-term Follow Ups
NCI CTCAE	National Cancer Institute Common Terminology for Adverse Events

NGHA	Ministry of National Guard – Health Affairs
NSAID	Nonsteroidal Anti-inflammatory Drugs
OPBG	Ospedale Pediatrico Bambino Gesù
OTC	Over the Counter
PCR	Polymerase Chain Reaction
PD	Pharmacodynamics
PK	Pharmacokinetics
pPK	Population PK
RFS	Relapse-Free Survival
RCR	Replication Competent Retrovirus
SAE	Serious Adverse Event
SUSAR	Serious Unexpected Serious Adverse Reaction
TCR	T-Cell Receptor
TK	Thymidine Kinase
TRM	Transplant-Related Mortality
VCN	Vector Copy Number

## 4 INTRODUCTION

### 4.1 BPX-501: Genetically Modified T Cells With Safety Switch

#### 4.1.1 iCasp9 Safety Gene

Unmodified donor T cell infusion is potentially an effective strategy for conferring anti-viral and anti-tumor immunity following allo-HSCT (Di Stasi 2011). However, the administration of greater than  $10^5$  cells/kg unmodified donor T cells to recipients of haploidentical stem cell transplantation has been associated with increased incidence of GVHD. It has been previously demonstrated that administration of up to  $10^7$  cells/kg of CD25+ allogeneic donor T cells after haploidentical transplantation for hematological malignancies could be administered safely and that the addition of these T cells was effective in controlling viral disease (Amrolia 2006). However, mortality due to disease relapse remained high, presumably due to the fact that the estimated frequency of tumor-reactive precursors is 1 to 2 logs lower than the frequency of virus- reactive precursors.

The use of higher numbers of allogeneic T cells containing an inducible caspase 9 safety gene in order to treat the potential increase in GVHD was then evaluated. The caspase recruiting domain of the human caspase 9 was modified with a drug binding domain, permitting T cell elimination after administration of a chemical dimerization drug, rimiducid. Administration of rimiducid dimerizes and activates caspase 9 which activates downstream caspases, leading to apoptosis potentially within minutes to hours (Di Stasi 2011, Tey 2007).

The gamma retrovirus, SFG.iCaspase9.2ADeltaCD19 (BPZ-1001), consists of inducible caspase 9 (iCasp9) linked, via a 2A-like sequence, to truncated human CD19 (DeltaCD19). The iCasp9 genetic modification, unlike the Herpes Simplex Virus (HSV)-TK based safety gene, is human derived and therefore likely to be less immunogenic. Moreover, pre-clinical and clinical studies show that killing occurs with much greater rapidity (within 3 hours) than with HSV-TK. Further advantages of the iCasp9 system are that killing induced by the dimerizer drug is primarily restricted to activated/proliferating cells, thus targeting donor alloreactive T cells active in GVHD, but sparing anti-viral donor T cells and potentially anti-tumor specific T cells. Additionally, administration of the commonly used drug, ganciclovir, is not precluded.

#### 4.1.2 Rimiducid Dimerizer Drug

Rimiducid is a member of a new class of lipid-permeable compounds termed activating, or dimerizer, drugs that act by inducing clustering of engineered proteins inside cells.

Rimiducid -inducible activation of the Caspase 9 safety gene is achieved by expressing a chimeric protein (iCasp9), fused to a drug-binding domain derived from human FK506-binding protein (FKBP). This chimeric protein is quiescent inside cells until administration of rimiducid, which cross-links the FKBP domains, initiating iCasp9 signaling. This signaling induces apoptosis of the gene modified cells. Rimiducid is formulated at [REDACTED]  
[REDACTED]

#### 4.1.3 CASPALLO Trial

In a Phase I study, ten patients between the ages of 3 and 17 years who had undergone stem-cell transplantation for relapsed acute leukemia were treated with the genetically modified T cells. The cells were detected in peripheral blood and increased in number over time, despite their constitutive transgene expression. A single dose of dimerizing drug, rimiducid, given to the patients in whom GVHD developed, eliminated more than 90% of the modified T cells within 30 minutes after administration and a greater than 90% reduction in CD19+ (i.e. transduced) T cells within 30 minutes of drug administration, and a further log reduction within 24 hours without any reports of infusion toxicity. Moreover, acute GVHD of the skin in all three patients, and of the liver disease in one patient, completely resolved after 24 hours. (Di Stasi 2011). The patients who developed GVHD received rimiducid. None of the 10 patients developed cGvHD. Six of the 10 patients are alive to date, with relapse as the primary cause of death in the other 4 patients (Zhou 2014).

The residual iCasp9 gene modified T cell population expanded over the next 4-14 days and continued to help repopulate the patients' immune systems. The transduced cells were further shown to contain virus and fungal-peptide specific precursor cells which had not caused further GVHD. When examined ex vivo, these non-alloreactive iCasp9 T cells remained susceptible to apoptosis following exposure to the dimerizer rimiducid. The authors concluded that a single dose of dimerizer drug could eliminate the subpopulation of T cells causing GVHD but could spare viral specific cytotoxic T lymphocytes (CTL)s.

The iCasp9 gene is most highly expressed in activated and proliferating T cells, such as those causing GVHD. If cells are not activated, due to lack of viral stimulation for example, expression of the transgene is lower and in a minority of these cells, iCasp9 levels are insufficient to induce apoptosis after single rimiducid dose exposure, allowing subsequent re-expansion (Berger 2004). This hypothesis was supported by the CASPALLO clinical data showing activation-dependent

induction of iCasp9 in T lymphocytes and enhanced susceptibility to dimerizer drug in activated versus resting T cells.

#### **4.2 Evaluation of Benefits/Risks**

The direct benefit for the patient will be to improve his clinical outcome in terms of successful eradication of disease, modulation of GVHD and speed of both hematopoietic and immune recovery.

The benefit for the community will be to potentially improve the clinical outcome of patients receiving a HLA-haplo-identical HSCT for the treatment of hematological disorders in terms of: promoting engraftment, lowering TRM and reducing the risk of disease recurrence, thus rendering the procedure more widely applicable.

The potential long term risk of gene therapy using a retroviral vector (although considered a rare risk) is the generation of replication competent retrovirus. While the vector has been constructed to minimize the risk of Replication Competent Retrovirus (RCR), which is therefore considered low risk and unlikely, the inclusion of the safety gene switch and potential to administer rimiducid to rapidly clear the product is a clear advantage of therapy.

### **5 OBJECTIVES OF THE STUDY**

#### **5.1 Primary Objective**

Overall Survival and incidence of Disease-Free Survival in both malignant and non-malignant patients at 1 and 2 years post-transplant. Relapse-Free Survival in malignant patients at 1 year and 2 years post-transplant.

#### **5.2 Secondary Objectives**

1. Long-term survival and safety for a total of 15 years from BPX-501 administration.
2. Assessment of PK (rimiducid) and PD (BPX-501) profiles after treatment with rimiducid for aGVHD.

#### **5.3 Estimated Enrollment**

Up to 175 patients who were previously treated on the BP-004 protocol.

#### **5.4 Subject Inclusion Criteria**

1. Signed written informed consent by the patient or the patient's guardian for children who are minors.

2. Enrolled on BP-004 protocol, received BPX-501 infusion, completed or discontinued from the study, and are beyond Day +180.

### **5.5 Subject Exclusion Criteria**

1. Lack of parents'/guardian's informed consent for children who are minors
2. Withdrawal from BP-004 study prior to BPX-501 infusion

## **6 PATIENT POPULATION AND SELECTION**

This study will enroll any infant (1 day - 23 months), child (2-11 years) or teenager (12-18 years) with malignant hematological disorders in complete morphological remission or non-malignant hematological disorders who did not have a HLA-matched sibling donor and was enrolled on BP-004 and received BPX-501 infusion. No patients between the age of 0-27 days are likely to be enrolled.

### **6.1 Patient Discontinuation/Withdrawal Criteria**

Patients and/or parent(s) or legal guardian(s) are free to discontinue participation or withdraw consent from the long term follow up study at any time, for any reason, and without prejudice to further treatment.

They may withdraw consent to future treatment with rimiducid, or from continuing participation in the LTFU. Patients with difficulty attending visits may stay on study, attend LTFU visits as they are able and remain eligible for rimiducid if needed.

Where possible patients will be encouraged to remain on-study and complete appropriate follow-up assessments.

If an adverse event (AE) is the reason the patient's treatment is being discontinued by the investigator or the reason that a patient chooses to discontinue treatment, then that adverse event must be documented as the reason for treatment discontinuation.

Patients who discontinue/withdraw from the study will receive treatment as deemed appropriate by their treating physician.

A patient's participation in the study also may be discontinued at any time at the discretion of the investigator. The following may be justifiable reasons for the investigator to remove a patient from the study:

- The patient was erroneously included in the long term follow up study.

Data of patients withdrawn from the study will be collected, stored and, whenever indicated, analyzed. These patients will be monitored in terms of outcome with particular regard to survival and, in case of malignancies, risk of recurrence.

If a patient is withdrawn from the study, the investigator should make reasonable effort to complete and report the observations as thoroughly as possible up to the date of withdrawal. All information should be reported on the appropriate case report forms. Data of patients withdrawn from the study will be evaluated, as detailed in the fully executed original consent signed by the patient/parent/guardian upon study entry, unless otherwise indicated. Where possible, these patients will be monitored in terms of outcome for survival and risk of recurrence. The patient/parent/guardian will be informed that follow-up testing or end of study procedures may be required to ensure patient safety is properly maintained.

Patients who have disease relapse or progression should continue to be followed on study to assess survival status and participate in long-term gene therapy monitoring, as appropriate.

Patients that cannot be contacted and who do not have a known reason for discontinuation will be classified as “lost to follow-up” with respect to the reason for discontinuation. The investigator’s study staff should make three documented attempts to contact the patient by telephone. If the patient cannot be reached by telephone, the investigator’s staff should attempt to contact the patient by certified mail or an alternative similar method, where appropriate.

## **7 DESIGN AND CONDUCT OF THE STUDY**

### **7.1 Trial Rationale**

This is a long-term follow-up study evaluating the safety of BPX-501 T cells infused after partially matched, related, T cell-depleted HSCT in pediatric patients previously enrolled on the BP-004 protocol who received BPX-501, completed or discontinued from the study and are beyond Day 180. The trial will evaluate the treatment of GvHD by the infusion of dimerizer drug (rimiducid) in those patients who present with cGvHD who progress or do not respond to standard of care treatment.

## 7.2 Trial Design

The BP-004 Phase I trial design consisted of 3 different escalating doses ( $2.5 \times 10^5$ ,  $5 \times 10^5$ ,  $1 \times 10^6$  cells/kg recipient total body weight) in all patient populations and further escalation of 2 doses ( $2 \times 10^6$ ,  $4 \times 10^6$  cells/kg recipient total body weight) were evaluated in patients with malignant disease only.

Patients were enrolled at the recommended dose for a maximum of 175 pediatric patients total (for both phases), and the minimum active study follow-up for each patient was 180 days in protocol BP-004.

Patients enrolled on the BP-004 study who received BPX-501 T-cells and are beyond Day 180 will be requested to enroll on this long-term follow up protocol, regardless of whether they completed or discontinued from the parent study BP-004.

The follow-up time for evaluation for overall survival and disease-free survival in patients with malignant disease and patients with non-malignant disease will be 1 and 2-years post-transplant. Relapse-free survival in malignant patients will be evaluated at 1 and 2 years. Long term follow-up for survival and gene therapy safety will be 15 years after BPX-501 treatment.

## 7.3 Patient Enrollment, Registration and Assignment to Treatment

Informed consent will be obtained from each patient and/or parent or guardian after the nature of the study is explained and prior to the performance of any study-specific procedures.

Upon enrollment into the study, the patient will continue with the same number assignment as assigned in BP-004.

## 7.4 Rimiducid Dimerizer Drug Packaging, Labeling and Storage

### 7.4.1 Packaging and Formulation

The Rimiducid for Injection is packaged in Type 1 clear glass serum vials (each 3 mL vial contains approximately 2 mL of drug product solution). The contents of each vial is composed [REDACTED]

[REDACTED]. Each vial is stoppered with a Teflon® coated serum stopper and a flip-off seal.

#### **7.4.2 Labeling**

The primary product label (applied directly to the vial) will contain all information for regional use, following the requirements of each competent authority and applicable national and international regulations as described in the pharmacy manual.

#### **7.4.3 Storage**

The rimiducid for Injection vials must be stored at  $5^{\circ}\text{C} \pm 3^{\circ}\text{C}$  ( $41^{\circ}\text{F} \pm 5^{\circ}\text{F}$ ) in a limited access, qualified refrigerator, preferably without light.

#### **7.4.4 Preparation for Treatment**

For use, the rimiducid will be diluted prior to administration. The rimiducid is administered via intravenous (IV) infusion at a dose of 0.4 mg/kg diluted in normal saline with volume as appropriate for age of patient to be administered over 2 hours, using a DEHP-free saline bag and solution set.

### **7.5 Infusion of Rimiducid**

#### **7.5.1 Chronic GVHD Treatment**

Chronic GVHD (cGVHD) typically occurs 100 days or later after HSCT. cGVHD can often present with a sicca-like syndrome with thickened skin, lichen planus, papules, cholestatic jaundice, scleroderma-like skin, eye and GI lesions. cGVHD patients can also develop obstructive pulmonary disease symptoms.

cGVHD is typically classified into mild (i.e., localized skin involvement, with/or without liver dysfunction) or moderate to severe (i.e., generalized skin involvement or localized skin and/or hepatic dysfunction, plus liver histology showing hepatitis/necrosis/cirrhosis, eye involvement, salivary gland involvement, or effects on other organs). Moderate to severe cGVHD usually involves more than one organ with an organ severity score of moderate or greater (or mild or greater for lungs). Management guidelines for cGVHD are shown in [Appendix B](#).

Response should be assessed per [Appendix B](#). Three general categories of overall response are used in clinical trials: complete response (CR), partial response (PR), and lack of response (unchanged, mixed response, progression). Complete response is defined as resolution of all manifestations in each organ or site, and partial response is defined as improvement in at least 1 organ or site without progression in any other organ or site. The 2014 NIH Consensus Working Group recommends that skin, mouth, liver, upper and lower GI, esophagus, lung, eye, and

joint/fascia be considered in evaluating overall response. Genital tract and other manifestations are not included due to lack of validated response measures.

Partial response in a specific organ requires an improvement of 1 or more points on a 4 to 7-point scale or an improvement of 2 or more points on a 10 to 12-point scale. The overall category of PR requires the absence of progression in any organ.

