## Appendix A.2: Response Determination for Chronic GvHD

Response Determination for Chronic GVHD Clinical Trials based on Clinician Assessments

Organ	Complete Response	Partial Response	Progression
Skin	NIH Skin Score 0 after previous involvement	Decrease in NIH Skin Score by 1 or more points	Increase in NIH Skin Score by 1 or more points, except 0 to 1
Eyes	NIH Eye Score 0 after previous involvement	Decrease in NIH Eye Score by 1 or more points	Increase in NIH Eye Score by 1 or more points, except 0 to 1
Mouth	NIH Modified OMRS 0 after previous involvement	Decrease in NIH Modified OMRS of 2 or more points	Increase in NIH Modified OMRS of 2 or more points
Esophagus	NIH Esophagus Score 0 after previous involvement	Decrease in NIH Esophagus Score by 1 or more points	Increase in NIH Esophagus Score by 1 or more points, except 0 to 1
Upper GI	NIH Upper GI Score 0 after previous involvement	Decrease in NIH Upper GI Score by 1 or more points	Increase in NIH Upper GI Score by 1 or more points, except 0 to 1
Lower GI	NIH Lower GI Score 0 after previous involvement	Decrease in NIH Lower GI Score by 1 or more points	Increase in NIH Lower GI Score by 1 or more points, except from 0 to 1
Liver	Normal ALT, alkaline phosphatase, and Total bilirubin after previous elevation of 1 or more	Decrease by 50%	Increase by 2 × ULN
Lungs	
 
- Normal %FEV1 after previous involvement
 
- If PFTs not available, NIH Lung Symptom Score 0 after previous involvement
 
	
 
- Increase by 10% predicted absolute value of %FEV1
 
- If PFTs not available, decrease in NIH Lung Symptom Score by 1 or more points
 
	
 
- Decrease by 10% predicted absolute value of %FEV1
 
- If PFTs not available, increase in NIH Lung Symptom Score by 1 or more points, except 0 to 1
 

Joints and fascia	Both NIH Joint and Fascia Score 0 and P-ROM score 25 after previous involvement by at least 1 measure	Decrease in NIH Joint and Fascia Score by 1 or more points or increase in P-ROM score by 1 point for any site	Increase in NIH Joint and Fascia Score by 1 or more points or decrease in P-ROM score by 1 point for any site
Global	Clinician overall severity score 0	Clinician overall severity score decreases by 2 or more points on a 0-10 scale	Clinician overall severity score increases by 2 or more points on a 0-10 scale

ULN indicates upper limit of normal.

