## Appendix A.3: Chronic GvHD Activity Assessment - Clinician

Date: \_\_\_\_\_

Subject Weight (kg): \_\_\_\_\_

SUBJECT ID: \_\_\_\_\_

CHRONIC GvHD ACTIVITY ASSESSMENT- CLINICIAN												
Health Care Provider Global Ratings:		Over the <4 time>, would you say that this patient's cGvHD is:										
0=none	1=mild	2=moderate	3=severe	0	1	2	3					
		When would you rate the severity of this patient's chronic GvHD symptoms on the following scale, where 0 is cGvHD symptoms that are not at all severe and 10 is the most severe cGvHD symptoms possible:										
		0	1	2	3	4	5	6	7	8	9	10
		cGvHD symptoms not at all severe									Most severe cGvHD symptoms possible	
											Over the <4 time>, would you say that this patient's cGvHD is:	
											4=1: Very much better	
											4=2: Moderately better	
											4=3: A little better	
											4=4: About the same	
											4=5: A little worse	
											4=6: Moderately worse	
											4=7: Very much worse	
Mouth		Erythema	None	0	Mild erythema or moderate erythema (<25%)	1	Moderate (26-50%) or Severe erythema (<25%)	2	Severe erythema (26-50%)	3		
		Lichenoid	None	0	Lichen-like changes (<25%)	1	Lichen-like changes (26-50%)	2	Lichen-like changes (>50%)	3		
		Ulcers	None	0			Ulcers involving (>20%)	3	Severe ulcerations (>20%)	6		
												Total score for all mucosal changes
Gastrointestinal-Esophageal		0= no esophageal symptoms 1=Occasional dysphagia or odynophagia with solid food or pills during the past week 2=intermittent dysphagia or odynophagia with soft foods or pills, but not for liquids or soft foods, during the past week 3=Dysphagia or odynophagia for almost all oral intake, on almost every day of the past week										
Gastrointestinal-Upper GI		0= no symptoms 1=infrequent, occasional symptoms, with little reduction in oral intake during the past week 2=moderate, intermittent symptoms, with some reduction in oral intake during the past week 3=more severe or persistent symptoms throughout the day, with marked reduction in oral intake, on almost every day of the past week										

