The resolution of acute GvHD (aGvHD) or chronic GvHD (cGvHD) after administration of rimiducid will be based on the response grading of the GvHD criteria provided in the protocol. The event for this endpoint is any patient who achieved a best overall response (BOR, i.e., either a Complete Response (CR) or Partial Response (PR)) based on aGvHD grading. Only patients experiencing aGVHD who received rimiducid (AP1903) infusion for treatment will be considered for this endpoint. Best overall resolution of aGVHD is defined from the date of AP1903 infusion. The percentage of patients with acute or chronic GvHD, the number of doses of rimiducid, and the best overall response to rimiducid within 7 and 30 days will be presented in listings and summarized. Concomitant medication usage in subjects with acute or chronic GvHD and, further, among those subjects who went on to receive rimiducid, will also be summarized.

Additional analysis and summary statistics will be conducted for resolution of chronic GvHD after administration of rimiducid as well as any case of GvHD (acute or chronic).

(iv) Immune reconstitution as determined by T cell subset counts at day 180

- a. Median and range of CD3 counts at 30, 60, 100 and 180 days
- b. Median and range of CD4 counts at 30, 60, 100 and 180 days
- c. Median and range of CD8 counts at 30, 60, 100 and 180 days

Quantitative assessment of each immune T-cell counts will be performed at various visit time points after transplant as captured in clinical database up to day 180 of follow-up. Analysis and statistical summaries will be performed separately for each T cell subtype assessed. The pattern of each immune reconstitution lab counts will be summarized using graphical summaries and descriptive statistic summary tables including mean (standard deviation), median, and range (minimum, maximum) across the time points assessed. Plots of mean and median cell counts representing measurements over time will be generated to visualize general patterns over time of immune reconstitution.

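### Section 7.5.1 sends readers to an appendix without response thresholds, and its point rule for partial response of chronic GVHD does not fit the Appendix A.2 criteria for liver and PFT-assessed lung

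*Protocol*

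**What the plan says.** Protocol Section 7.5.1 lists the organs considered for overall response, liver and lung among them. Overall partial response (PR) is improvement in at least one organ with no progression in another. For a single organ, "Partial response in a specific organ requires an improvement of 1 or more points on a 4 to 7-point scale". A second threshold covers measures with a longer range: "an improvement of 2 or more points on a 10 to 12-point scale". No exception is made for organs followed by laboratory values or lung function. On where to look, the section says "Response should be assessed per" Appendix B. Appendix B covers management, sampling times and the forms to complete, and sets no threshold for complete response, PR or progression.

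Appendix A.2 is the response-determination table. Its liver PR is "Decrease by 50" per cent. Its lung PR is "Increase by 10% predicted absolute value of %FEV1", with a 1-point fall in the symptom score accepted only when PFTs are unavailable. Its mouth PR is "Decrease in NIH Modified OMRS of 2 or more points".

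Protocol Section 10.4.5.3 reports chronic GVHD response rates at 6 months in patients given rimiducid. SAP Section 6.4.2(iii) says that resolution after rimiducid "will be based on the response grading of the GvHD criteria provided in the protocol".

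**The concern.** Section 7.5.1 reads as a complete rule: it uses the word requires, never cites Appendix A.2, and points to a different appendix. Appendix A.1 carries 0 to 3 scores for liver and lung, so someone working from Section 7.5.1 has four-level scales to which the rule can be applied. Someone working from Appendix A.2 would use the percentage fall and the FEV1 gain instead. Because one improved organ is enough for overall PR, the choice can decide whether a patient counts as a responder. Two sites, or a site and the analysis programmer, could classify the same patient differently.

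**Working it through.** The plan states no figure on this point, so there is none to reproduce. The check compares the two rules row by row, then classifies a few illustrative patients.

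**Step 1. Section 7.5.1 against Appendix A.2**

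| Measure | Section 7.5.1 | Appendix A.2 PR | Agree? |
|---|---|---|---|
| Skin, eyes, esophagus, upper GI, lower GI | 1 point | 1 point | Yes |
| Joints and fascia | 1 point | 1 point on the score, or on P-ROM at any site | Yes |
| Lung, no PFTs | 1 point | 1 point on the symptom score | Yes |
| Mouth (OMRS) | 2 points | 2 points | Yes |
| Global 0-10 score | 2 points | 2 points | Yes |
| Lung, PFTs available | only a point rule is stated | +10 in % predicted FEV1 | No |
| Liver | only a point rule is stated | 50% fall | No |

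Mouth takes the long-scale rule because the Appendix A.3 form sums erythema (up to 3), lichenoid change (up to 3) and ulcers (up to 6): 3 + 3 + 6 = 12.

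**Step 2. Can liver and lung be classified differently?**

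Inputs: Appendix A.1 liver bands (normal; below 2; 2 to 5; above 5 x ULN) and FEV1 bands (above 80; 60-79; 40-59; 39 or less). The patient values are assumed, not trial data. The liver rows assume that the one enzyme shown sets the liver score.

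- Point rule: PR if the Appendix A.1 score falls by at least 1.
- Appendix A.2 liver: PR if (before - after) / before is at least 50%.
- Appendix A.2 lung: PR if after - before is at least 10.

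| Before to after | A.1 score | PR by points | A.2 calculation | PR by A.2 |
|---|---|---|---|---|
| ALT 5.5 to 4.0 x ULN | 3 to 2 | Yes | 1.5 / 5.5 = 27% | No |
| ALT 4.8 to 2.3 x ULN | 2 to 2 | No | 2.5 / 4.8 = 52% | Yes |
| ALT 4.5 to 1.9 x ULN | 2 to 1 | Yes | 2.6 / 4.5 = 58% | Yes |
| FEV1 58% to 61% | 2 to 1 | Yes | +3 | No |
| FEV1 41% to 55% | 2 to 2 | No | +14 | Yes |
| FEV1 55% to 66% | 2 to 1 | Yes | +11 | Yes |

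The rules can disagree in either direction for these two organs, and they can also agree. Each disagreement depends on applying the Section 7.5.1 rule to the Appendix A.1 scores.

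**Step 3. When does it reach the reported rate?** Only when liver or PFT-assessed lung alone decides PR. If a point-scored organ also improves and none progresses, both pages give a PR.

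**The case against.** The strongest reply is that Section 7.5.1 merely summarises Appendix A.2 and leaves out its two non-point rows. Much supports this. The section's organ list follows Appendix A.2: esophagus, upper GI and lower GI are separate and the genital tract is excluded, whereas Appendix A.1 has one GI row and includes the genital tract. Appendix A.1 is a grading scale, and Section 7.5.1 does not cite it for response. The Appendix A.3 clinician form, which Appendix B asks for, records bilirubin, ALT, alkaline phosphatase and FEV1. It has no 0 to 3 liver score, and its lung score is by symptoms. Table 1 (footnote 6) also sends readers to Appendix A as well as Appendix B for GVHD assessment.

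This makes Appendix A.2 the likely intention, so the defect is an omission with a wrong cross-reference more than a clash across organs. It does not remove the defect. Section 7.5.1 never says that it is a summary, allows no exception for laboratory or lung-function measures, and names the wrong appendix.

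A reader might infer three stronger points that the documents do not support:

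- **Mouth also conflicts.** It does not. The OMRS maximum is 12, so the 2-point threshold is the second half of the Section 7.5.1 sentence.
- **The SAP leaves the choice between these two passages open.** The SAP states that it is based on the BP-004 protocol, which is not among the documents, so its reference to protocol criteria does not clearly mean BP-404. It also defines the response event by acute GVHD grading and treats chronic GVHD as additional analysis.
- **Repeat dosing hinges on the formal PR definition.** Appendix B gives partial response only as an example of clinical improvement.

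**Conclusion.** The point holds for two organs, liver and PFT-assessed lung, and for the cross-reference to Appendix B. All point-scored rows agree. A patient whose only improvement is in one of the two organs can be classed differently, provided the Section 7.5.1 rule is applied to the Appendix A.1 scores.

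A reader might go on to infer a material shift in the response rate. The documents cannot support any figure: they give no count of rimiducid-treated chronic GVHD patients, no organ mix and no distribution of ALT or FEV1 change. The examples show that reclassification is possible, not how often it would occur. The affected result is the descriptive response rate in Section 10.4.5.3; overall, disease-free and relapse-free survival do not depend on it. Severity is minor, but the correction is worth making because a stated rule can misclassify responders.

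**What to change.** - **Protocol Section 7.5.1:** cite Appendix A.2 in place of Appendix B for response. State that the 1-point and 2-point rules apply to point-scored organs, and that liver and PFT-assessed lung follow their Appendix A.2 rows, using values recorded on the Appendix A.3 form.
- **SAP Section 6.4.2(iii):** add a sentence naming which protocol's response table governs complete and partial response of chronic GVHD for data from BP-404 (Tables 14.2.4.2 to 14.2.4.4).
- **Appendix B:** the sponsor should state which definition its partial-response example refers to. No clinical rule is proposed here.

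The cost is a short protocol clarification and one SAP sentence. No new data are needed, since the Appendix A.3 form already captures the liver values and FEV1.
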